10.3. Appendix 3: Assessment Windows

10.3.1. Definitions of Assessment Windows for Analyses

No Assessment Windows will be defined for Analysis, and summaries and analyses will be based on nominal visits.

10.4. Appendix 4: Study Phases and Treatment Emergent Adverse Events

10.4.1. Study Phases

Assessments and events will be classified according to the time of occurrence relative to the start and/or stop date/time of the study treatment within the period for Part A and the start and/or stop date/time of the study treatment for Part B.

Study Phase	Definition
Pre-Treatment	Date/Time ≤ Study Treatment Start Date/Time
On-Treatment	Study Treatment Start Date/Time < Date/Time ≤ Study Treatment Stop Date/Time
Post-Treatment	Date/Time > Study Treatment Stop Date/Time

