Treatment Period	Cohort 1 will comprise of three treatment periods, investigating three dosing regimens. Each dose regimen consists of 1 day treatment duration, with subjects in house for 4 nights (through at least 48 hours post-last dose). Subjects will be admitted to the unit the day before dosing, will remain in the unit overnight, and will be released following completion of the assessments on Day 4 of each treatment period, provided there are no safety concerns.
Washout Period	Will be at least 7 days between dose regimens for an individual subject.
Follow-up	At least 7 days and no greater than 14 days after last study drug administration. If warranted, additional follow-up visits may be scheduled.

Study Duration – Cohort 2

Screening	Approximately 28 days.
Number of Subjects	One Cohort of 12 subjects (N=12).
Treatment Period	The treatment duration will be 14 days. Subjects will be admitted to the unit the day before dosing, will remain in the unit overnight and will be released following completion of the assessments on Day 17, provided there are no safety concerns.
Follow-up	At least 7 days and no greater than 14 days after last study drug administration. If warranted, additional follow-up visits may be scheduled.

Study Duration – Cohorts 3, 4 and 5

Screening	Approximately 28 days.
Number of Subjects	Three Cohorts of 14 subjects each (N=42).
Treatment Period	The treatment duration will be 14 days. Subjects will be admitted to the unit the day before dosing, will remain in the unit overnight and will be released following completion of the assessments on Day 17, provided there are no safety concerns.
Follow-up	At least 7 days and no greater than 14 days after last study drug administration. If warranted, additional follow-up visits may be scheduled.

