2.2. Time and Events Table – Part B (Cohorts 2-5)

Procedure	Screening (Up to 28 days before Day 1)	Study Period (Days)																	Follow-up (No more than 14 days post last dose)	Notes	
		-1	1	2	3	4	5	6	7	8	9	10	11	12	13	14	15	16			17
Outpatient Visit	X																			X	
Admission to Clinical Unit		X																			
Inpatient Stay at Clinical Unit			←-----X-----→																		
Discharge from Clinical Unit																			X	Following completion of all assessments.	
Informed Consent	X																				
Inclusion and Exclusion Criteria	X																				
Demography	X																				
Full Physical Examination	X																		X	Additional exams/screens may be performed, or brief exams made full exams, by the Investigator, as deemed necessary (e.g. where safety or laboratory findings indicate). Tests will be conducted within site specified standards.	
Brief Physical Examination		X		X		X				X									X		
Height	X																				
Weight	X								X										X		
Drug/Alcohol/Smoking Screen	X	X																		Tests include alcohol breath test, smoking breath test and urine drug screen.	
Medical/Medication/Drug/Alcohol History	X																				
HIV, Hepatitis B and	X																				

Procedure	Screening (Up to 28 days before Day 1)	Study Period (Days)																	Follow-up (No more than 14 days post last dose)	Notes			
		-1	1	2	3	4	5	6	7	8	9	10	11	12	13	14	15	16			17		
C Screening																							
Tuberculosis Test	X																						
Anti-Nuclear Antibody	X								X												X		
Serum Pregnancy Test (WOCBP only)	X																					X	
Urine Pregnancy Test (WOCBP only)		X																			X		
Highly effective contraceptive method (WOCBP only)	X	X	X	X	X	X	X	X	X	X	X	X	X	X	X	X	X	X	X	X	X	X	Must use method for a minimum of 28 days prior to first dose of study medication until the follow-up visit.
Contraception with male condoms (WOCBP using hormonal contraceptive method and male subjects with female partners of childbearing potential only)		X	X	X	X	X	X	X	X	X	X	X	X	X	X	X	X	X	X	X	X	X	
C-SSRS	X	←X→							X											X	X ^c	May be completed on either Day -1 or Day 1, but no later than 1hr prior to dosing. To be completed pre-dose on Day 7. ^c C-SSRS to be conducted on follow-up only in the instance that a subject withdraws from the study.	
Meals		X	X	X	X	X	X	X	X	X	X	X	X	X	X	X	X	X	X	X	X	X	TID Dosing: On Day 1 through 14 subjects will fast 8hr overnight. Breakfast will be served approximately

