9.3.6. Suicidal Risk Monitoring

GSK2982772 is considered to be a CNS-active drug. There is some concern that some CNS-active drugs may be associated with an increased risk of suicidal thinking or behaviour when given to some subjects. Although this drug has not been shown to be associated with an increased risk of suicidal thinking or behaviour when given to healthy volunteers, GSK considers it important to monitor for such events before or during clinical studies with compounds such as this.

Participants being treated with GSK2982772 should be monitored appropriately and observed closely for suicidal ideation and behaviour or any other unusual changes in behaviour. All subjects who experience signs of suicidal ideation or behaviour must immediately be discontinued from study medication.

Families and caregivers of participants being treated with GSK2982772 should be alerted about the need to monitor participants for the emergence of unusual changes in behaviour, as well as the emergence of suicidal ideation and behaviour and to report such symptoms immediately to the study investigator.

At screening and baseline (pre-dose Day 1) in Part B only, the Baseline/Screening assessment of suicidal ideation and behaviour and treatment emergent suicidal ideation and behaviour will be monitored during study 205184 using C-SSRS. At Days 7 and 17 of the study, the 'Since Last Visit C-SSRS' will be completed. Refer to Section 2, SoA, for more information.

Subjects who answer 'Yes' to any suicidal behaviour or 'Yes' to suicidal ideation Questions 4 or 5 will be referred to their General Practitioner (GP) or appropriate

psychiatric care. The medical monitor will be notified. If appropriate, an AE or SAE should be reported (see Section 9.1). In addition, the investigator should complete a Possible Suicidality Related Adverse Event (PSRAE) form to collect detailed information on the circumstances of the reported AEs which, in the investigator's opinion, are possibly suicidality-related. These may include, but are not limited to, an event involving suicidal ideation, a preparatory act toward imminent suicidal behaviour, a suicide attempt, or a completed suicide.

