2.41.	Safety (Part B)	CSSRS1	Summary of Subjects with C-SSRS Suicidal Ideation or Behaviour during Treatment (Part B)		SAC	

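### If Table 2.41 selects on the SAP's study phases, the Part B C-SSRS summary omits the Day 17 form and rests on a form that follows only 43% of doses

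*SAP*

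**What the plan says.** SAP 10.4.1 sets the phases: "Assessments and events will be classified according to the time of occurrence relative to the start and/or stop date/time of the study treatment". On-treatment is "Study Treatment Start Date/Time < Date/Time ≤ Study Treatment Stop Date/Time" and post-treatment is "Date/Time > Study Treatment Stop Date/Time". The section contains no lag and no special rule for the C-SSRS. The one-day allowance in SAP 10.4.2 is for adverse events only. SAP 10.3.1 defines no assessment windows and works from nominal visits.

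For Part B, the Protocol synopsis states: "The treatment duration will be 14 days". Protocol 9.3.6 gives the post-baseline schedule: "At Days 7 and 17 of the study, the 'Since Last Visit C-SSRS' will be completed". The Part B schedule (Protocol 2.2) adds for the first of these: "To be completed pre-dose on Day 7". The same schedule provides a follow-up C-SSRS only for a subject who withdraws.

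The summary display is Table 2.41 in SAP 10.10.5, titled "Summary of Subjects with C-SSRS Suicidal Ideation or Behaviour during Treatment (Part B". It cites shell CSSRS1 and has no programming note. SAP 6.3 refers C-SSRS analyses to the sponsor's core data standards unless otherwise specified. Listings 74 and 75 (SAP 10.10.10) present the Part B C-SSRS data with no stated phase restriction.

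**The concern.** A Since Last Visit form reports on a stretch of time that ends when the form is completed. Classifying it by its completion date assigns that whole stretch to whatever phase the completion date falls in. In Part B the second form is completed three days after dosing ends but looks back into the dosing period. A rule based on the form's own date/time therefore calls it post-treatment.

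The protocol treats the drug as CNS-active and lists suicidality as a potential risk in Protocol 3.3.1, noting reports of depressed mood and abnormal dreams in the first-in-human study. With 9 active subjects planned per cohort, one positive form is the difference between a zero and a non-zero cell. A reader of Table 2.41 would take a zero to mean that nothing was reported across 14 days of dosing, when the table might rest on a form completed before the Day 7 dose.

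**Working it through.** The plan gives no figure to reproduce here, so the check places the planned doses and forms on one time axis and applies the 10.4.1 inequalities.

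**Inputs.** First dose on Day 1 is hour 0, and the first dose on Day d is at 24 × (d − 1). TID doses fall at 0, 7 and 14 h and BID doses at 0 and 12 h, on Days 1 to 14 (Protocol 5.1 and synopsis). C-SSRS is pre-dose on Day 7 and on Day 17 (Protocol 9.3.6 and 2.2).

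**Last dose.** TID: 13 × 24 + 14 = 326 h. BID: 13 × 24 + 12 = 324 h.

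**Day 7 form.** It is completed shortly before 6 × 24 = 144 h. That is after 0 h and before 324 or 326 h, so it is on-treatment for a subject who continues dosing.

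**Day 17 form.** The nominal hour is 16 × 24 = 384 h. The clock time is not specified; assuming any time from 8 h before to 16 h after the nominal hour gives 376 to 400 h.
- TID: 376 − 326 = 50 h to 400 − 326 = 74 h after the last dose.
- BID: 376 − 324 = 52 h to 400 − 324 = 76 h after the last dose.

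It is post-treatment throughout that range.

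**Doses preceding the Day 7 form.**
- TID: 6 × 3 = 18 of 14 × 3 = 42 doses, 42.9%; the remaining 24 of 42 are 57.1%.
- BID: 6 × 2 = 12 of 14 × 2 = 28 doses, 42.9%; the remaining 16 of 28 are 57.1%.

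Measured in time for TID, Day 7 to the last dose is 7 × 24 + 14 = 182 h out of 326 h, or 56%, much the same share. SAP 5.1 notes that the Cohort 5 dose level was not required, so the TID figures are the ones that matter in practice.

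**Would the adverse-event allowance help?** No. The stop date is Day 14; adding one day reaches Day 15. Day 17 is the stop date plus 3 days, so lags of 0, 1 or 2 days exclude it.

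**Two further cases under the same rule.**
- A withdrawn subject's follow-up form is completed 7 to 14 days after the last dose, so it is post-treatment.
- Protocol 9.3.6 requires immediate discontinuation on signs of suicidal ideation or behaviour. If a Day 7 pre-dose form is positive and dosing stops there, the last dose was on Day 6, at 5 × 24 + 14 = 134 h (TID) or 5 × 24 + 12 = 132 h (BID). The form, at about 144 h, is then some 10 or 12 h after the stop time and is itself post-treatment.

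**The case against.** The strongest reply is that nothing connects SAP 10.4.1 to Table 2.41. The table has no programming note, SAP 6.3 sends C-SSRS displays to a sponsor standard, and shell CSSRS1 is not in the documents and may define the period differently. The title may also be template wording: Table 2.20 uses the same words for Part A, where no C-SSRS is scheduled. SAP 10.3.1 works by nominal visit, and 10.4.1 speaks of events as well as assessments, so ideation on Day 10 could be said to have occurred on treatment even if recorded on Day 17. The recall window is an inference too, because Protocol 9.3.6 does not define the last visit and subjects are inpatients throughout.

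Much of this stands. It makes the exclusion conditional, and it makes the 57% depend on reading the last visit as the Day 7 form. It does not show that the table is safe. SAP 10.4.1 is the only treatment-phase definition the SAP gives for assessments, and a programmer who follows it produces the wrong table. Nor do the documents say that onset dates within the recall period are captured, which classifying by event date would require.

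A reader might infer that second-week suicidality findings would vanish from the report. The documents do not support that. Listings 74 and 75 show no phase restriction. Protocol 9.3.6 provides for an AE or SAE report where appropriate, and discontinuation is required, so the AE and disposition tables could also show such a subject. Those routes are only a partial backstop for the C-SSRS summary, because AE reporting is discretionary.

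Finally, counting the whole Day 17 form attributes about 3 off-drug days to treatment, and up to 14 for a withdrawal form. That is a real cost, but it errs on the cautious side for a safety display.

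**Conclusion.** Wrong as written, on the condition that Table 2.41 uses the 10.4.1 phases. On that condition, a completer contributes only the Day 7 pre-dose form, which follows 43% of planned doses. Taking the last visit as the Day 7 form, the remaining 57% are covered only by a form the table leaves out. Follow-up forms from withdrawn subjects, and positive Day 7 forms that lead to stopping, would be left out as well.

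It would be too strong to say that the SAP definitely excludes the Day 17 form, because no text ties the table to the phase and the standard shell cannot be seen. What is certain is narrower: the only phase rule stated for assessments gives the wrong class to a recall form completed after the last dose, and the SAP states no exception. The percentages are shares of dosing, not of expected events; the documents give no event rate.

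**What to change.** Add one sentence to SAP 10.4.1, or as a programming note to Table 2.41, along these lines:

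*All post-baseline Since Last Visit C-SSRS forms (Day 7, Day 17 and any early-withdrawal follow-up form) are counted, because their recall period includes treatment days; a footnote states that the recall extends about 3 days (up to 14 days for withdrawal forms) beyond the last dose.*

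With the Day 17 form counted, and on the same reading of the last visit, the table covers 42 of 42 TID doses or 28 of 28 BID doses for a completer. Naming the forms is better than extending the phase by a fixed lag: one or two days would not reach Day 17, and three days would still miss the withdrawal forms.

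The cost is one sentence, one footnote and a programming flag. Listings 74 and 75, data collection and study conduct need no change.

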10.4.1.1. Study Phases for Concomitant Medications

Treatment State	Definition
Prior	If medication end date is not missing and is before 28 days prior to screening visit
Concomitant	Any medication that is not a prior
NOTES	· · · · · · · · · · · · · · · · · · ·

NOTES:

 Please refer to Appendix 7: Reporting Standards for Missing Data for handling of missing and partial dates for concomitant medication. Use the rules in this table if concomitant medication date is completely missing

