7.6. Concomitant Therapy

Any medication or vaccine (including over-the-counter or prescription medicines, vitamins, and/or herbal supplements) that the participant is receiving at the time of enrolment or receives during the study must be recorded along with:

- reason for use
- dates of administration including start and end dates
- dosage information including dose and frequency

The Medical Monitor should be contacted if there are any questions regarding concomitant or prior therapy.

Participants must abstain from taking prescription or non-prescription drugs (including vitamins and dietary or herbal supplements) within 7 days (or 14 days if the drug is a potential enzyme inducer) or 5 half-lives (whichever is longer) before the start of study treatment until completion of the follow-up visit, unless, in the opinion of the investigator and sponsor, the medication will not interfere with the study.

Paracetamol at doses of ≤ 2 grams/day, is permitted for use any time during the study. Other concomitant medication may be considered on a case-by-case basis by the Investigator in consultation with the Medical Monitor if required.

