1.9.	Safety (Part A)	DM5	Summary of Race and Racial Combinations (Part A)	ICH E3, FDA, FDAAA, EudraCT	SAC
Part A	(Cohort 1 – sing	gle ascending dos	e, 3-way crossover): Medical Conditions and Prior and Concor	nitant Medications	
1.10.	Safety (Part A)	MH1 / MH4	Summary of Current/Past Medical Conditions (Part A)	ICH E3 Separate summaries for Current & Past conditions, if collected.	SAC
1.11.	Safety (Part A)	CM1	Summary of Concomitant Medications (Part A)	ICH E3	SAC
Part A	Cohort 1 – sing	gle ascending dos	e, 3-way crossover): Exposure and Treatment Compliance	·	
1.12.	Safety (Part A)	EX5	Summary of Exposure to Study Treatment (Part A)	ICH E3 Total daily dose (mg) and number of days	SAC
Part B	(Cohorts 2, 3, 4	and 5 – repeat do	se, sequential-group): Subject Disposition		
1.13.	Safety (Part B)	ES1	Summary of Subject Disposition for the Subject Conclusion Record (Part B)	ICH E3, FDAAA, EudraCT	SAC
1.14.	Safety (Part B)	SD1	Summary of Treatment Status and Reasons for Discontinuation of Study Treatment (Part B)	ICH E3	SAC

Study I	Population Tabl	les			
No.	Population	IDSL / Example Shell	Title	Programming Notes	Deliverable [Priority]
1.15.	All Subjects (Part B)	ES6	Summary of Screening Status and Reasons for Screen Failure (Part B)	Journal Requirements	SAC
Part B	(Cohorts 2, 3, 4	and 5 – repeat do	se, sequential-group): Protocol Deviation	·	
1.16.	Safety (Part B)	DV1	Summary of Important Protocol Deviations (Part B)	ICH E3	SAC
Part B	(Cohorts 2, 3, 4	and 5 – repeat do	se, sequential-group): Population Analysed		
1.17.	Safety (Part B)	SP1	Summary of Study Populations (Part B)	IDSL Add the following footnotes: [1] Subjects are included in the Randomised population if they were randomly assigned to treatment in the study. [2] Subjects are included in the Safety population if they have been randomized and received at least one dose of study treatment. [3] Subjects are included in the Pharmacokinetic population if they are in the Safety Population and a pharmacokinetic sample was obtained and analysed.	SAC

Study F	Population Tab	les			
No.	Population	IDSL / Example Shell	Title	Programming Notes	Deliverable [Priority]
Part B	Cohorts 2, 3, 4	and 5 – repeat do	se, sequential-group): Demographic and Baseline Characterist	ics	
1.18.	Safety (Part B)	DM1	Summary of Demographic Characteristics (Part B)	ICH E3, FDAAA, EudraCT Do not include Weight (to be included in Vital Signs summary) [1] For calculating age, birth date is imputed as June 30 in the year of birth.	SAC

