1.19.	Randomised (Part B)	DM11	Summary of Age Ranges (Part B)	EudraCT Only include age ranges applicable to the study ('Adult (18-64 years)' and '>=65-84 years'))	SAC
1.20.	Safety (Part B)	DM5	Summary of Race and Racial Combinations (Part B)	ICH E3, FDA, FDAAA, EudraCT	SAC
Part B	Cohorts 2, 3, 4	and 5 – repeat do	se, sequential-group): Medical Conditions and Prior and Conco	omitant Medications	
1.21.	Safety (Part B)	MH1 / MH4	Summary of Current/Past Medical Conditions (Part B)	ICH E3 Separate summaries for Current & Past conditions, if collected.	SAC
1.22.	Safety (Part B)	CM1	Summary of Concomitant Medications (Part B)	ICH E3	SAC
Part B	Cohorts 2, 3, 4	and 5 – repeat do	se, sequential-group): Exposure and Treatment Compliance		
1.23.	Safety (Part B)	EX1	Summary of Exposure to Study Treatment (Part B)	ICH E3 Total daily dose, cumulative actual dose and number of days.	SAC

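### The SAP's Prior/Concomitant split is tied to screening, not first dose, so medicines stopped before dosing are counted as concomitant in Tables 1.11 and 1.22

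*SAP*

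**What the plan says.** SAP section 10.4.1.1 has two lines. A medicine is Prior "If medication end date is not missing and is before 28 days prior to screening visit". A medicine is Concomitant if it is "Any medication that is not a prior". Neither line mentions the date of study treatment, and no other SAP text narrows them.

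The medication summaries in SAP section 10.10.4 are Table 1.11, "Summary of Concomitant Medications (Part A"), and Table 1.22, "Summary of Concomitant Medications (Part B"). No summary of prior medicines is listed, although the group headings above both tables refer to prior as well as concomitant medications.

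The protocol's Schedule of Activities puts screening "Up to 28 days before Day 1". Protocol section 7.6 requires participants to abstain from medicines "within 7 days (or 14 days if the drug is a potential enzyme inducer) or 5 half-lives (whichever is longer") ahead of dosing and on through to follow-up, unless the drug is judged not to interfere. Exclusion criterion 12 sets the same interval. Section 7.6 also states which medicines go on record: those the participant is "receiving at the time of enrolment or receives during the study must be recorded".

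**The concern.** A reader of a concomitant-medication table takes it to show what participants were using while on study drug. Here the dividing line is 28 days before screening, so the table also counts drugs that were gone before the first dose. The effect is systematic, because the protocol itself asks participants to stop most medicines between screening and dosing and requires the medicines they were taking at enrolment to be recorded.

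The rule is also out of step with its neighbours. SAP section 10.4.1 classifies assessments and events by study treatment start and stop, and section 10.4.2 flags treatment-emergent adverse events from treatment start. Only medicines are classified from screening, and no reason is given.

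What is at stake is how the tables read. The protocol's risk assessment names P-glycoprotein inhibitors as able to raise study drug levels and says concomitant medication will be monitored for interactions. As defined, Tables 1.11 and 1.22 cannot separate a drug present during dosing from one stopped to meet the washout.

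**Working it through.** The plan states no figure to reproduce, so the check applies the rule literally.

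**Inputs**
- S = days from screening to Day 1; at most 28 (Schedule of Activities, both parts).
- K = days from the medicine's end date to first dose.
- Prior if the end date is earlier than screening minus 28 days (SAP 10.4.1.1).

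**Rule restated.** An end date K days before dosing is K − S days before screening. It is Prior if K − S > 28, that is K > S + 28. It is Concomitant if K ≤ S + 28.

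| Screening (days before Day 1) | Longest gap from stop to first dose still Concomitant |
|---|---|
| 1 | 1 + 28 = 29 days |
| 7 | 7 + 28 = 35 days |
| 14 | 14 + 28 = 42 days |
| 21 | 21 + 28 = 49 days |
| 28 | 28 + 28 = 56 days |

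With screening 28 days before Day 1, Prior starts at 57 days.

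**Washout stops.** For any S of at least 1 the limit is at least 29 days. Stops at 7, 14 or 28 days before dosing are therefore Concomitant whatever the screening date.

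**Which of these records are certain to be in the data**
- Drug taken at screening, stopped before dosing: K ≤ S ≤ 28. Section 7.6 requires it to be recorded, and K ≤ S is always below S + 28, so it is always Concomitant.
- Drug stopped in the 28 days up to screening: S < K ≤ S + 28, at most 56. It is Concomitant if recorded. Section 7.6 does not require a drug that ended before enrolment to be recorded. Medication history is taken at screening, but the documents do not say whether it feeds these tables.
- Drug stopped earlier than that: K > S + 28. It is Prior.

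**Direction of error.** A medicine that ended on or after first dose has K ≤ 0, which is below S + 28, so it is Concomitant. A missing end date is also Concomitant. No medicine used during dosing is lost.

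**Partial dates.** The SAP's rules for partial dates set an incomplete stop date to the latest possible day and month. That pushes records in the same direction.

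**Rule tied to first dose.** With Prior meaning K ≥ 1, end dates 7, 14, 28, 29, 30, 42, 56 and 57 days before dosing all become Prior. Medicines that ended on or after first dose, or have no end date, stay Concomitant.

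**The case against.** The strongest reply is that neither document defines concomitant as taken with study treatment. Section 7.6 is headed Concomitant Therapy and covers medicines received at enrolment, and the Schedule of Activities places the concomitant medication review at screening as well as later. On that usage, a drug taken at screening and stopped before Day 1 is concomitant therapy, and the SAP rule is a broad but reproducible convention. This has force as an account of what is collected. It does not fully explain the rule, because a drug stopped in the 28 days before screening is neither received at enrolment nor received during the study, yet the rule calls it Concomitant. Nor does it help a reader of the tables separate pre-dose from on-treatment use.

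Other displays also limit the harm, and that stands. Listings 11 and 50 give subject-level concomitant-medication data. Important protocol deviations are summarised (Tables 1.5 and 1.16) and listed (Listings 6 and 45), and eligibility deviations, which would include Exclusion 12, are listed (Listings 7 and 46). Those displays, rather than Tables 1.11 and 1.22, identify breaches of the medication restrictions.

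A third reply concerns the remedy. Because no prior-medication table is planned, changing the cut-off alone would remove pre-dose medicines from every summary, including a potential inducer stopped shortly before dosing. That is correct, and the fix has to allow for it.

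**Conclusion.** The point holds as a minor one. The rule is explicit, and it places medicines stopped before dosing in tables titled as concomitant use. The supported size is stops up to 28 days before first dose, for drugs being taken at screening. The ceiling is 56 days, which needs screening 28 days before Day 1 and a CRF that captures drugs stopped before screening. The documents give no basis for estimating how many participants or records are involved.

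Three stronger readings are tempting and not supported:
- **Every washed-out drug is miscounted.** The washout is 5 half-lives where that is longer. A drug stopped more than 56 days before dosing is always Prior.
- **On-treatment use could be missed.** The rule errs only by inclusion, so no medicine taken during dosing drops out of the tables.
- **PK, CYP3A4-marker or adverse event results are affected.** SAP section 5.4 plans no covariates or subgroups, and no planned analysis of these endpoints uses the flag. The effect stops at two descriptive tables.

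**What to change.** In SAP section 10.4.1.1, define Prior as a medicine whose end date is before the first dose of study treatment (first dose of Period 1 in Part A). Define Concomitant as any use from first dose to the follow-up visit, with missing end dates staying Concomitant.

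At the same time, retitle Tables 1.11 and 1.22 as Prior and Concomitant Medications and give each separate Prior and Concomitant rows. Pre-dose medicines, including those stopped shortly before dosing, then stay visible under the right label.

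The cost is one derivation change, a line of SAP text, two title changes and slightly longer tables. No data collection changes.
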